ARDS is a highly heterogeneous syndrome, characterized by diverse etiologies, inflammatory phenotypes, and morphologic patterns. This heterogeneity is reflected in its physiologic features, imaging manifestations, underlying causes, timing of onset, biomarker profiles, and genetic variation. The causes of ARDS can be broadly categorized into two groups: pulmonary and extrapulmonary. Pulmonary causes—such as pneumonia and ventilator-associated injury—primarily damage the alveolar epithelium, while extrapulmonary causes—such as sepsis and severe acute pancreatitis—initially injure the vascular endothelium and subsequently lead to pulmonary edema^[14]. Consequently, personalized therapeutic strategies must be grounded in a deep understanding of ARDS pathophysiology, a complexity that has contributed to the relatively slow progress in ARDS management. Moreover, early in the disease course, clinical manifestations may be subtle in a subset of patients, making it critical to identify which individuals are at higher risk of progressing to severe disease and experiencing major complications, including death^[15,16].

Pulmonary imaging is a critical tool for assessing the morphologic and mechanical characteristics of ARDS. Compared with standard chest radiography or lung ultrasound, chest CT offers substantially higher sensitivity and specificity. Lung ultrasound, while

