widely accessible, may increase the false-positive rate in ARDS diagnosis due to its high sensitivity to interstitial infiltration and consolidation^[17]. Quantitative analysis of ARDS-related CT scans allows measurement of non-aerated, poorly aerated, well-aerated, and over-aerated lung tissue, leading to the concepts of the “baby lung” and the lung “sponge model”^[18]. These quantitative approaches reveal the redistribution of lung density in the prone position and changes in the fraction of non-aerated lung under different airway pressures, representing the gold standard for assessing lung recruitability and guiding mechanical ventilation strategies^[19]. Similarly, in certain conditions such as thoracic trauma, early CT quantification of parenchymal injury can help predict the temporal evolution from initial focal or diffuse alveolar hemorrhage to typical ARDS patterns of pulmonary edema and interstitial alteration^[20]. However, since the mid-1980s, the clinical use of quantitative CT analysis has remained limited because it requires manual image processing by clinicians^[21]. Moreover, evaluating lung recruitability can take 6–8 hours and is subject to measurement variability. These limitations highlight the urgent need for new or more intelligent technologies to facilitate accurate, efficient, and standardized quantitative assessment while reducing operator-dependent bias.

With the advancement of artificial intelligence (AI) technology, its role in healthcare systems is increasingly being realized. Broadly defined, AI refers to a machine or computational platform capable of making intelligent decisions in a manner analogous to human reasoning. Currently, AI shows promising applications across various fields including radiology, pathology, ophthalmology, cardiology, and oncology^[22–24]. It is widely utilized in drug discovery, disease diagnosis, healthcare planning, health monitoring, digital consultation, surgical intervention, clinical data management, personalized treatment, and decision support^[25]. Compared with conventional technologies, AI offers several advantages, such as faster detection, reduced burden on healthcare professionals, enhanced productivity, efficiency, accuracy, and precision, lower medical costs, and improved quality of care^[25, 26].

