Advances in AI-enabled deep learning for CT image analysis allow automated identification of parenchymal lung changes, quantitative segmentation of hypo-ventilated or high-density regions, and integration with clinical data to build predictive models. Incorporating multicentre data can improve model generalizability and address the performance decline often observed in external validation of single-centre studies, thereby supporting the development of robust and reliable intelligent auxiliary strategies for ARDS diagnosis and management. Indeed, the high mortality associated with ARDS stems not only from inadequate management strategies but also from challenges in early detection, risk stratification, and severity prediction. Consequently, developing AI-assisted diagnostic and management tools represents a pressing need, particularly for critical conditions such as ARDS [29–31].

Therefore, this study proposes a multicentre retrospective investigation integrating data from 400 ARDS cases across three tertiary comprehensive hospitals. Through standardized image preprocessing and rigorous modeling approaches, we aim to develop and validate a CT-imaging-driven model for ARDS grading and clinical decision support, assess its cross-centre stability, and ultimately provide a generalizable intelligent tool for clinical practice.

Primary Objective

To develop an intelligent assessment model for ARDS severity using multicentre chest CT data. By integrating quantitative CT features with clinical characteristics, the

model aims to predict short-term major clinical events (such as decisions regarding mechanical ventilation, prone positioning strategy, mortality, and ECMO use), stage and quantify the disease, and establish a diagnostic and risk-stratification model for ARDS to assist in guiding therapeutic strategies.

Secondary Objective

To validate the generalizability of the model across external centres and evaluate its applicability in multicentre real-world settings; and to analyze the influence of different centres and CT scanner models on imaging features and model performance.

The overall research design and plan

This was a retrospective, multicenter, observational cohort study.

Study population

This study planned to enroll a total of 400 ARDS patients admitted to the intensive care units of three comprehensive tertiary hospitals.

Inclusion Criteria

1. Patients meeting the **2023 global updated definition of ARDS**.

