2. Admission to the **Intensive Care Unit (ICU) for more than 48 hours**.
3. Availability of **chest CT imaging data**.

Exclusion Criteria

1. Patients aged <18 years.
2. Patients with incomplete medical records.
3. Absence of chest CT imaging or presence of technically inadequate/uninterpretable chest CT images.

Sample Size and Data Partitioning

This study is designed as a multicenter, large-sample, retrospective observational study and plans to include a total of 400 patients with ARDS who meet the eligibility criteria. Of these, 300 cases will be contributed by the primary institution and Sub-center 1, and 100 cases by Sub-center 2.

The study does not involve conventional experimental or control groups. Instead, cases will be partitioned into three datasets according to the model development workflow:

Training set: 276 cases (approximately 80% of the combined cases from the primary institution and Sub-center 2), obtained through stratified random sampling to preserve the distribution of mild, moderate, and severe ARDS;

Internal validation set: 69 cases (approximately 20% of cases from the same two centers), used to monitor overfitting and optimize model hyperparameters;

External test set: 55 cases, all derived from Sub-center 1 and entirely independent of the model development process, used to evaluate model generalizability.

Primary Outcome Measures

The primary outcomes of this study focus on the overall effectiveness of the proposed AI-based framework across three key clinical tasks:

(1) Accuracy of ARDS severity classification, defined as the agreement between model-predicted ARDS severity (mild, moderate, or severe) and the reference clinical classification based on the 2023 global ARDS criteria, assessed using chest CT images obtained within 24 hours of ICU admission;

(2) Treatment plan matching rate, defined as concordance between model-recommended and actual clinical management across five intervention modalities (mechanical ventilation, high-flow oxygen therapy, non-invasive ventilation, prone positioning, and neuromuscular blockade), evaluated at the time of index chest CT acquisition;

(3) Accuracy of 28-day in-hospital mortality prediction, defined as the ability of the model to predict all-cause in-hospital mortality within 28 days of ICU admission.

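### ARDS onset is not tied to ICU admission, although the severity CT and the 28-day mortality clock both start there, so ARDS that begins after the admission scan can be paired with a pre-onset image and add days in which death could not occur

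*Combined protocol and SAP*

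**What the plan says.** All references are to the combined protocol and SAP.

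- **Eligibility.** Inclusion Criteria require the "2023 global updated definition of ARDS", admission to the "Intensive Care Unit (ICU) for more than 48 hours" and availability of "chest CT imaging data". None of the three says when ARDS must be present. The Exclusion Criterion on imaging covers only "Absence of chest CT imaging or presence of technically inadequate/uninterpretable chest CT images". Nothing excludes ARDS acquired in the ICU.
- **Primary outcome 1 (severity).** The model's grade is compared with a "reference clinical classification based on the 2023 global ARDS criteria, assessed using chest CT images obtained within 24 hours of ICU admission". The scan has a time window; the reference grade has none.
- **Primary outcome 3 (mortality).** The model is to "predict all-cause in-hospital mortality within 28 days of ICU admission".
- **Data collection (Research procedures, item 1).** PaO2 and FiO2 are listed without sampling times. No ARDS onset date or time is listed.
- **Introduction.** Pulmonary causes of ARDS are described as "such as pneumonia and ventilator-associated injury". For conditions such as thoracic trauma, the text says that "early CT quantification of parenchymal injury can help predict the temporal evolution from initial focal or diffuse alveolar hemorrhage to typical ARDS patterns".

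**The concern.** The anchor for the scan and the mortality clock is ICU admission, but the event that makes a patient eligible may come later. The study is retrospective, so ARDS status over the whole stay is known when cases are selected. Two problems follow for a patient whose ARDS begins after the admission scan.

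For outcome 1, the image predates the disease being graded. If the reference grade is taken at or after onset, the pair is a forecast of later severity, not a grading of current severity. If it is taken at the time of the scan, there is no ARDS yet to grade. Either way, accuracy has no single meaning once such cases are mixed with ARDS present at admission, and the mixing can enter training as well as testing.

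For outcome 3, the patient had to survive to onset to be included. The days before onset count towards the 28 but could not contain a death. Calibration of the mortality model is a secondary outcome and cross-centre generalizability is the secondary objective; calibration may shift if the late-onset share differs by centre.

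This is separate from late scanning. It arises even when every CT is taken within 24 hours of admission.

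**Working it through.** **1. The plan's own figure.** Sample size estimation gives at most 15 predictors, 10 events per predictor and about 37.5% in-ICU mortality. 15 × 10 = 150 deaths; 150 / 0.375 = 400. The stated total reproduces and is not in dispute here.

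**2. The timing rules side by side.**

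| Element | Time stated |
|---|---|
| ARDS criteria met | none |
| ICU stay | more than 48 h |
| CT for eligibility | none |
| CT for outcome 1 | within 24 h of ICU admission |
| Reference severity grade | none |
| Mortality clock | 28 days from ICU admission |

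With onset on ICU day d, where d is after the scan, the patient satisfies every rule, the scan precedes ARDS, and only 28 − d days of the window can contain a death.

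**3. Size for mortality (illustration only).** Assumptions: constant hazard, and 37.5% mortality over 28 days from ARDS onset. The 37.5% is the protocol's in-ICU figure used as a proxy. Survival over t days is then 0.625^(t/28).

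The stay rule means that every included patient survived about 2 days on this clock, including those with ARDS at admission. The right comparator is therefore 1 − 0.625^(26/28) = 35.4%, not 37.5%.

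| Onset | Days at risk | Counted mortality, 1 − 0.625^((28−d)/28) | Gap from 35.4% |
|---|---|---|---|
| Day 3 | 25 | 34.3% | 1.1 points |
| Day 7 | 21 | 29.7% | 5.7 points |
| Day 8 | 20 | 28.5% | 6.9 points |
| Day 14 | 14 | 20.9% | 14.4 points (from unrounded values) |

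The post-onset hazard is identical in every row; only the count differs.

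**4. Size for the whole cohort.** Assume 10-30% late onset (the documents give no figure). The effect is that share times the gap.

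- Onset on day 3: 0.1 to 0.3 points against 35.4%; 0.3 to 1.0 points against 37.5%.
- Onset on day 7: 0.6 to 1.7 points against 35.4%; 0.8 to 2.3 points against 37.5%.
- Onset on day 14: 1.4 to 4.3 points against 35.4%.

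So for onset by day 7 the cohort effect stays within about 2.4 points on either comparator.

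**5. Patients affected.** 10-30% of 400 is 40 to 120. Of the 55 external test cases it is 5.5 to 16.5, or about 6 to 17. For outcome 1 these are upper limits: only late-onset patients who also had a CT within 24 h of admission are mis-paired. Eligibility asks for any CT, and the plan does not say what happens to a patient scanned only later.

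**The case against.** The best defence is that ARDS around admission was intended. The Study population section speaks of ARDS patients admitted to ICUs, etiology is listed with the baseline data, and the severity scan belongs to the first 24 hours. That reading is plausible. But the wording is descriptive and sets no window, and a retrospective case-finder applying the criteria literally would include a patient who first met the definition on day 8. If ARDS at admission was meant, one sentence would say so.

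It can also be said that death within 28 days of ICU admission is a well-defined endpoint and admission a legitimate time zero. That is so when eligibility is known at admission. Here it may depend on a later event.

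Several stronger readings are tempting, and the documents do not support them:

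- **That late onset is common.** The Introduction lists ventilator-associated injury as a cause and describes trauma scans evolving over time. Its remark that extrapulmonary causes injure the endothelium first concerns the order of tissue injury, not ICU timing. Together these show that later onset is possible, not how often it occurs.
- **That image and label are certainly mismatched.** The grading time is unstated, so a late grade on an early scan is one possible implementation.
- **That later onset will be made to look protective.** Onset time is neither collected nor named as a predictor, so the plan makes no such comparison.
- **That calibration will shift.** It may, if the late-onset share differs between centres; nothing shows that it does.

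**Conclusion.** The point holds as a design gap. As written, the rules admit ARDS that begins after the admission scan, attach it to a scan and a clock that start before onset, and collect nothing that would let the analyst identify those patients afterwards.

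The size is unknown because the late-onset share and onset times are not given. Under the stated assumptions, the distortion of counted mortality within the late-onset group is small for onset on day 3 (about 1 point), moderate on day 8 (about 7 points) and large only near day 14. A reader comparing 28.5% with 37.5% might infer a 9-point gap on day 8; about 2 points of that come from the 48-hour stay rule, which applies to everyone. The whole-cohort effect is modest for onset by day 7. The more consequential part is outcome 1, where the meaning of accuracy is at issue and a handful of cases matters in a test set of 55. The change should be made; the illustration does not demonstrate that results will be biased.

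**What to change.** 1. Add to the data collection list the date and time at which ARDS criteria were first met, abstracted from existing charts.
2. Define the index CT as the scan within 24 hours of ICU admission used for outcome 1, and take the reference severity grade from the PaO2/FiO2 closest to it.
3. Limit the primary analysis of outcomes 1 and 3 to patients who meet ARDS criteria within 24 hours of the index CT, and name one time zero for eligibility, scan, grade and the 28-day count. With the CT within 24 hours of admission, onset then falls no later than 24 + 24 = 48 hours after admission, so no survival is guaranteed beyond what the stay rule already imposes.
4. Report later-onset patients separately or in a sensitivity analysis, describing their scan as a predictor of later severity. State how patients without a CT in the window are handled.

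The cost is one extra chart variable, a few sentences of protocol text and a primary set for outcomes 1 and 3 that shrinks by the late-onset share. The guaranteed survival of about 2 days from the stay rule remains and should be acknowledged when mortality is reported. If the team prefers a lighter change, an explicit onset window in the Inclusion Criteria and a stated time for the reference grade would close most of the gap, but the onset time would still be needed to apply that window.

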These three outcomes collectively reflect the overall effectiveness of the model within a closed-loop framework encompassing disease stratification, treatment recommendation, and prognosis prediction.

Secondary Outcome Measures

Secondary outcomes include comparative performance improvement of the proposed model over commonly used baseline AI models; calibration performance of mortality prediction; interpretability analyses based on imaging-derived and clinical feature contributions; and assessment of the association between treatment concordance and 28-day in-hospital mortality using multivariable regression models.

Research procedures

1. Data collection

(1) Demographic and Baseline Clinical Data

Age, sex, body mass index (BMI), comorbidities (including chronic kidney disease, coronary artery disease, hypertension, diabetes, liver cirrhosis, HIV infection, etc.), primary etiology of ARDS, and receipt of mechanical ventilation, high-flow nasal oxygen therapy, or ECMO. BMI is calculated as weight (kg) divided by height squared (m^2).

(2) Physiologic Parameters

Body temperature (T), heart rate (HR), respiratory rate (RR), peripheral oxygen saturation (SpO_2), and mean arterial pressure (MAP).

(3) Laboratory Parameters

pH, partial pressure of arterial oxygen (PaO_2), fraction of inspired oxygen (FiO_2), partial pressure of arterial carbon dioxide (PCO_2), lactate (Lac), platelet count (PLT), white blood cell count (WBC), hemoglobin (Hb), serum creatinine, C-reactive protein (CRP), procalcitonin (PCT), international normalized ratio (INR), B-type natriuretic peptide (BNP), and interleukin-6 (IL-6).

(4) Ventilator or High-Flow Oxygen Parameters

Positive end-expiratory pressure (PEEP), tidal volume (TV), plateau pressure (Pplat), and flow rate (FLOW).

(5) Other Clinical Scores

Sequential Organ Failure Assessment (SOFA) score and Acute Physiology and Chronic Health Evaluation II (APACHE II) score.

2. CT Equipment and Scanning Parameters

Chest CT images included in this study were acquired from two CT scanners with the following parameters:

CT1 (64-slice): Manufacturer: Philips; Model: Brilliance; Tube voltage: 120 kV; Tube current: 1000 mA; Slice thickness: 5 mm; Slice interval: 5 mm; Pitch: 0.789:1.

CT2 (128-slice): Manufacturer: United Imaging; Model: uCTR760; Tube voltage: 120 kV; Tube current: 1000 mA; Slice thickness: 5 mm; Slice interval: 5 mm; Pitch: 0.984:1.

3. Quantitative Assessment of ARDS

Preliminary Image Processing

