The sample size was preliminarily estimated using the event-per-variable principle. The mortality prediction component is designed to include no more than 15 candidate predictors in the final multivariable logistic regression model. Following the commonly accepted criterion of at least 10 outcome events per predictor, a minimum of 150 death

events is required to ensure model stability and interpretability. Based on historical data from the participating centers, the in-ICU mortality rate among patients with ARDS is approximately 37.5%. Accordingly, the total target sample size for this study is estimated to be approximately 400 patients.

Statistical Analysis Plan

All eligible cases will be stratified and randomly sampled at an 8:2 ratio within Shanghai General Hospital and its affiliated centers to form the model training set and internal validation set. Cases from an additional participating center will be reserved as an independent external test cohort.

Model performance will be evaluated for three predefined tasks: ARDS severity classification, treatment strategy prediction, and mortality risk prediction. Performance metrics will include accuracy, balanced accuracy, area under the receiver operating characteristic curve (AUC), precision–recall curve analysis, and the Brier score. During model development, five independent repeated experiments will be conducted, and performance will be reported as mean values with standard deviations.

For comparative performance assessment, results from the five independent experiments will be compared using two-sided Wilcoxon rank-sum tests, with a significance threshold of 0.05. Different levels of statistical significance will be denoted using conventional symbols (e.g., “*”, “**”) corresponding to predefined P-value ranges.

To assess the association between model outputs and clinical outcomes, model-recommended intervention sets will first be encoded for agreement with actual clinical management. These agreement variables will then be incorporated into multivariable logistic regression models together with six imaging-derived anatomical features (e.g., diaphragmatic height, lung volume). Adjusted odds ratios with 95% confidence intervals will be reported, and a two-sided P value <0.05 will be considered statistically significant.

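### Primary outcome 2 scores treatment at the time of the CT, so the matching rate supports a claim of concordance with concurrent care, not of predicting decisions or recommending treatment

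*Combined protocol and SAP*

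**What the plan says.** All references are to the combined protocol and SAP.

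- **Primary Objective.** The model "aims to predict short-term major clinical events (such as decisions regarding mechanical ventilation, prone positioning strategy, mortality, and ECMO use" among them) and is meant to help guide therapy.
- **Primary Outcome Measures, item (2).** The treatment plan matching rate is "defined as concordance between model-recommended and actual clinical management across five intervention modalities", and it is "evaluated at the time of index chest CT acquisition". The modalities are mechanical ventilation, high-flow oxygen, non-invasive ventilation, prone positioning and neuromuscular blockade.
- **Primary Outcome Measures, closing paragraph.** The three outcomes together are said to cover "disease stratification, treatment recommendation, and prognosis prediction".
- **Statistical Analysis Plan.** The task is named "treatment strategy prediction". For the association analysis, "model-recommended intervention sets will first be encoded for agreement with actual clinical management", with no time attached.

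The other two primary outcomes are anchored more firmly. Item (1) is "assessed using chest CT images obtained within 24 hours of ICU admission". Item (3) has a forward window of 28 days from ICU admission. Item (2) has neither a limit on when the index CT is taken nor a window after it.

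**The concern.** Predicting a decision requires a target that lies after the information used to predict it. Here the only time given for the target is that of the scan. Some patients will already be on a modality when scanned. For them, a match may mean only that the model recognised a treatment in progress. For others the decision is still open, and a match would carry forward information. The matching rate pools the two groups.

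What is at stake is the conclusion that primary outcome 2 can carry. A high rate would be reported as evidence that the tool recommends treatment or predicts strategy, when the defined measurement shows agreement with care at the moment of imaging.

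**Working it through.** **1. The plan's own figure.** The only sample-size calculation (Sample size estimation) reproduces: 15 predictors × 10 events = 150 deaths, and 150 / 0.375 = 400 patients. It concerns the mortality model. The plan gives no target value, precision or sample size for the matching rate, so there is no figure to test for this outcome.

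**2. Timing, side by side.**

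| Place | What is claimed or measured | Time of the target |
|---|---|---|
| Primary Objective | Prediction of short-term events, including treatment decisions | After the prediction, by implication |
| Primary outcome (2) | Agreement with actual management | At the index CT |
| Closing paragraph of the primary outcomes | Treatment recommendation | None stated |
| Statistical Analysis Plan | Treatment strategy prediction; agreement coding | None stated |
| Primary outcome (3), for comparison | In-hospital death | 28 days from ICU admission |

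No section supplies a later treatment window, so the time in outcome (2) governs. Scope differs too: ECMO is in the objective but not among the five modalities.

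**3. Inputs.** Under Data collection, receipt of ventilation, high-flow oxygen or ECMO and the ventilator or flow settings are recorded without a time stamp. Under Etiological and Respiratory Mechanics Classification, respiratory mechanics feed the extended model. The inputs of the treatment task are not listed, so these fields are neither confirmed as inputs nor barred.

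**4. Why the rate alone cannot separate the two parts (illustration; both inputs assumed).** Let *s* be the share of patients whose treatment is in place at the CT and recognisable (match = 1), and *m* the match rate for decisions still open. Then

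observed rate = *s* + (1 − *s*) × *m*.

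With *m* = 0.60:

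- *s* = 0: 0.60
- *s* = 0.25: 0.25 + 0.75 × 0.60 = 0.70
- *s* = 0.50: 0.50 + 0.50 × 0.60 = 0.80
- *s* = 0.75: 0.75 + 0.25 × 0.60 = 0.90

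At *s* = 0.50, *m* from 0.50 to 0.70 gives 0.75 to 0.85. An observed 0.70 arises equally from *s* = 0, *m* = 0.70 and from *s* = 0.25, *m* = 0.60. The documents give neither *s* nor *m*.

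**5. Majority-class check.** For a binary modality, always answering no has sensitivity 0 and specificity 1, so balanced accuracy is (0 + 1) / 2 = 0.50. Its AUC is also 0.50.

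**6. Patients left for a new-start analysis.** Take the 55 external cases stated in Sample Size and Data Partitioning, and assume that 50% to 80% already receive a given modality. Those still at risk of starting it number 55 × 0.50 = 27.5 down to 55 × 0.20 = 11, so about 27 to 11. New starts would be fewer still.

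**The case against.** The best defence is that the time of the CT is meant as the decision point, with the management chosen there as the reference. That reading is possible. The text does not state it, and if it is intended, the reference window still has to be written down. It does mean that a reader should not infer that every match reflects care already running, or that decisions made on the basis of the scan are certainly left unscored.

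Four further inferences are tempting, and the documents do not support them:

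- **Always answering no would look nearly perfect.** The Statistical Analysis Plan lists balanced accuracy, AUC and precision–recall analysis for all three tasks. A constant answer scores 0.50 on the first two. What remains is that the matching rate has no formula and that reporting by modality is not promised. No section gives the frequency of any modality at the scan.
- **Leakage is established.** It is possible, because nothing bars the treatment and ventilator fields, but the inputs of the task are not listed.
- **Removing ventilator settings would achieve nothing.** This is not shown. If the inputs do not reveal the treatment, agreement means that the model reached the clinicians' choice from lung involvement and physiology. That is legitimate cross-sectional concordance. The Introduction does say that management influences the clinical picture and that prone position and airway pressure alter CT findings, so the images might carry traces of treatment. How far they do is unknown.
- **The regression of 28-day mortality on concordance is biased by the same fault.** It uses the same agreement variable, so its label needs the same care. It is described as an association, however, and concordance fixed at the CT precedes later death. No bias follows from the timing alone.

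There is also a fair objection to making new starts the sole primary target. That would discard decisions to continue treatment and leave few external patients. This stands, and it is why the new-start analysis is proposed as an addition.

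**Conclusion.** The point holds in a limited form. Followed as written, primary outcome 2 measures agreement with concurrent care. It cannot by itself support a claim that the model predicts treatment decisions or recommends treatment, which is how the Primary Objective, the closing paragraph of the primary outcomes and the Statistical Analysis Plan present it. This is more than missing detail, because it changes what may be concluded from a primary outcome.

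The size of the effect cannot be computed from the documents. The rates in step 4 of the working rest on assumed values and on perfect matching among recognisable treatments. They show that the two components cannot be told apart, not that the rate is inflated by any particular amount. The conclusion does not depend on leakage. The study can proceed, but the outcome should be relabelled and supplemented before results are interpreted.

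**What to change.** 1. Define the index CT for outcome 2. Limit the model inputs to data available by that time, and exclude fields that directly record the treatment being predicted.
2. Label the at-CT matching rate as concordance with concurrent care, and do not interpret it as recommendation or prediction.
3. Add a separate pre-specified analysis of modalities newly started within one fixed window after the index CT, among patients not already receiving them. Base any claim about predicting decisions on this analysis.
4. Report each modality separately against its majority-class rate, alongside the metrics already listed.

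**Cost.** Start times must be extracted from charts; no new patients or procedures are needed. Follow-up should not be an obstacle. Eligibility requires more than 48 hours in ICU, so if the index CT falls in the first 24 hours, a 24-hour window (given only as an example) ends within the stay. The new-start analysis will be imprecise, above all in the external set, and should be reported with intervals. It would still not show whether a recommendation is correct. These changes concern outcome definition and timing only.
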